## 1 GENERAL INFORMATION

This protocol describes the Ad4HIV trial and provides information about procedures for entering participants into it. The protocol should not be used as an aide-memoire or guide for the treatment of other patients. Every care has been taken in drafting this protocol, but corrections or amendments may be necessary. These will be circulated to the registered investigators in the trial.

### COMPLIANCE

The trial will be conducted at the clinical site in compliance with the approved protocol, the Principles of Helsinki (2008), the principles of Good Clinical Practice (GCP), Commission Directive 2005/28/EC with the implementation in national legislation in the UK by Statutory Instrument 2004/1031 and subsequent amendments, the UK Data Protection Act (DPA number: Z5886415), and the National Health Service (NHS) Research Governance Framework for Health and Social Care (RGF).

## FUNDING

UK MRC

## AUTHORISATIONS AND APPROVALS

This protocol will not be implemented until approvals have been received from all the necessary regulatory and ethical bodies.

## TRIAL REGISTRATION

This trial has been registered in the EudraCT database where it is identified as 2016-000052-94.

### SAE REPORTING AND IMPORTANT AE NOTIFICATION

Within 24 hours of becoming aware of an SAE or important AE, please complete the SAE form, and email the coordinating centre (Clinical Trials Manager) to notify on:  

### SAE REPORTING AND IMPORTANT AE NOTIFICATION

**POSSIBLE SERIOUS BREACH NOTIFICATION**

Within 24 hours of becoming aware of a possible serious breach, please complete the Protocol Deviation Form, and email the coordinating centre (Clinical Trials Manager) to notify on:  

## 2 SUMMARY OF TRIAL

Summary Information Type	Summary Details
ACRONYM (or short Title of Trial)	Ad4HIV
Long Title of Trial	Ad4HIV: A Phase I Single-Blind randomised trial investigating immunisation strategies using Ad4-EnvCN54, MVA-CN54 and CN54gp140/MPLA combinations in order to maximise antibody responses to Human Immunodeficiency Virus
Version	6.0
Date	20 Dec 2018
EudraCT	2016-000052-94
REC Reference	17/LO/0302
IRAS ID	186866
Rationale and Methodology	
This is a randomised two part Phase I study which will explore the impact of different boosting options (MVA-C and protein) for oral Adenovirus serotype 4 vector prime expressing HIV-1 CN54 envelope (Ad4-EnvCN54) designed to optimize systemic and mucosal antibody response. The participants will be blind to the dose administered and the laboratory staff will be blind to the regimen throughout.
 
Part 1 is exploratory and designed to select conditions capable of promoting enhanced systemic and mucosal B cell responses in a limited number of participants.
 
Part 2 is dependent upon Part 1 and is designed to study groups selected on performance in part 1 in an expanded number of subjects. Data from both stages will be combined for safety and immunological analyses.

Investigational Products	
 
1) Ad4-EnvCN54 encoding CN54 envelope
 
2) MVA-C encoding CN54 gp120
 
3) CN54gp140: recombinant HIV-1 subtype C trimeric envelope protein adjuvanted in monophosphoryl lipid A (MPLA) and lyposomes
 
4) Placebo 1: Capsule administered orally to match Ad4-EnvCN54
 
5) Placebo 2: Buffered saline administered by I.M needle injection
 

Summary Information Type	Summary Details																																								
Type of Participants to be Studied	
Healthy male or female adults, 18 to 50 years of age, at low risk for HIV infection, who are available for the duration of the trial. They must be willing to undergo HIV testing, use an effective method of contraception. They must, in the opinion of the principal investigator or designee, understand the study and who provide written informed consent.
 
Principal exclusion criteria include confirmed HIV-1 or HIV-2 infection, preexisting Ad4 serum neutralising antibodies, pregnancy and lactation, significant acute or chronic disease, clinically significant laboratory abnormalities, recent vaccination or receipt of a blood product, previous receipt of an HIV vaccine, previous severe local or systemic reactions to vaccination or history of severe allergic reactions.
																																								
Study Design	
Part 1
 
The study will enrol 48 participants to Part 1. Recruitment will select potential participants who are willing to undergo serial blood draws and mucosal secretion sampling. Additional participants may be enrolled to replace any early withdrawals.
 
Vaccine & Immunisation Schedule for Part 1 & Part 2
 
Table 1
 
  
 Group	N	Month 0	Month 3	Month 6	
   
 A	6	Oral placebo	CN54gp140 +Oral placebo +I.M placebo	CN54gp140 +Oral placebo +I.M placebo	
 
 B	6	Ad4-EnvCN54	CN54gp140 +Oral placebo +I.M placebo	CN54gp140 +Oral placebo +I.M placebo	
 
 C	6	Ad4-EnvCN54	CN54gp140 + Ad4-EnvCN54 + I.M placebo	CN54gp140 +Oral placebo + I.M placebo	
 
 D	6	Ad4-EnvCN54	CN54gp140 + Ad4-EnvCN54 +I.M placebo	CN54gp140 + Ad4-EnvCN54 +I.M placebo	
 
 E	6	Oral placebo	CN54gp140 +MVA-CN54 +Oral placebo	CN54gp140 +MVA-CN54 +Oral placebo	
 
 F	6	Ad4-EnvCN54	CN54gp140 +MVA-CN54 +Oral placebo	CN54gp140 +MVA-CN54 +Oral placebo	
 
 G	6	Ad4-EnvCN54	CN54gp140 +MVA-CN54	CN54gp140 +MVA-CN54	
  
	Group	N	Month 0	Month 3	Month 6	A	6	Oral placebo	CN54gp140 +Oral placebo +I.M placebo	CN54gp140 +Oral placebo +I.M placebo	B	6	Ad4-EnvCN54	CN54gp140 +Oral placebo +I.M placebo	CN54gp140 +Oral placebo +I.M placebo	C	6	Ad4-EnvCN54	CN54gp140 + Ad4-EnvCN54 + I.M placebo	CN54gp140 +Oral placebo + I.M placebo	D	6	Ad4-EnvCN54	CN54gp140 + Ad4-EnvCN54 +I.M placebo	CN54gp140 + Ad4-EnvCN54 +I.M placebo	E	6	Oral placebo	CN54gp140 +MVA-CN54 +Oral placebo	CN54gp140 +MVA-CN54 +Oral placebo	F	6	Ad4-EnvCN54	CN54gp140 +MVA-CN54 +Oral placebo	CN54gp140 +MVA-CN54 +Oral placebo	G	6	Ad4-EnvCN54	CN54gp140 +MVA-CN54	CN54gp140 +MVA-CN54
Group	N	Month 0	Month 3	Month 6																																					
A	6	Oral placebo	CN54gp140 +Oral placebo +I.M placebo	CN54gp140 +Oral placebo +I.M placebo																																					
B	6	Ad4-EnvCN54	CN54gp140 +Oral placebo +I.M placebo	CN54gp140 +Oral placebo +I.M placebo																																					
C	6	Ad4-EnvCN54	CN54gp140 + Ad4-EnvCN54 + I.M placebo	CN54gp140 +Oral placebo + I.M placebo																																					
D	6	Ad4-EnvCN54	CN54gp140 + Ad4-EnvCN54 +I.M placebo	CN54gp140 + Ad4-EnvCN54 +I.M placebo																																					
E	6	Oral placebo	CN54gp140 +MVA-CN54 +Oral placebo	CN54gp140 +MVA-CN54 +Oral placebo																																					
F	6	Ad4-EnvCN54	CN54gp140 +MVA-CN54 +Oral placebo	CN54gp140 +MVA-CN54 +Oral placebo																																					
G	6	Ad4-EnvCN54	CN54gp140 +MVA-CN54	CN54gp140 +MVA-CN54																																					

			+ Ad4-EnvCN54	+Oral placebo
H	6	Ad4-EnvCN54	CN54gp140 +MVA-CN54 + Ad4-EnvCN54	CN54gp140 +MVA-CN54 + Ad4-EnvCN54
	48			

Participants will be randomised for recruitment into groups A-H in Part 1. The number of Ad4-EnvCN54 administrations combined with either gp140 protein boosts (A-D) or co-administration of gp140 with MVA-CN54 (E-H) will vary. Groups A (CN54gp140 alone) and E (MVA-CN54/CN54gp140 alone) will serve as control groups to assess the added benefit of the Ad4 vector. Following completion of Part 1, each vaccine group (A-H) will be assessed for number of mucosal responders (mucosal antibody (rectal/genital/oral) as measured by ELISA), and titre (mucosal and systemic) of antigen specific binding antibody. The primary immunogenicity endpoint will be Week 26; Visit 9. The vaccine groups and regimes (one from B-D and one from F-H) that have the best positive response at this timepoint will be expanded in Part 2 of the study.

Based on data from the MUCOVAC2 study, in which participants received 3 intramuscular doses of CN54gp140 with GLA-AF adjuvant, we anticipate that there will be no mucosal responders in group A (although there will be detectable systemic IgG responses). Enrollment through to completion of the primary immunological assessment for each group will be 7 months.

**Vaccine Schedule for Part 2**

The study will enrol an additional 12 participants to Part 2. The best regimes from A-D (Ad4-EnvCN54 / CN54gp140) and F-H (Ad4-EnvCN54 / MVA-CN54 / CN54gp140) will be expanded to n=12. Immunogenicity data will be analysed in 32 participants at week 26 (Primary Immunogenicity Endpoint). The study design for Part 2 will be the same as that used for Part 1 (Table 1: Vaccine and Immunisation Schedule) for the best responding groups only.

Selection will be based on total number of responders. In the event that more than one group has the same number of responders, mucosal antibody titre will be used to rank groups to determine which to take forward to Part 2. Should mucosal titers be indistinguishable between groups, then serum antibody levels will be taken into consideration in the selection of groups to progress to Part 2. The criterion for a positive mucosal response, and methods for ranking groups on the basis of mucosal and serum antibody titers, will be specified in the Laboratory Analysis Plan (LAP). If any group is associated with unacceptable product related adverse events, it will be discontinued from further study.

The decision to progress any group to Part 2 will be taken by the Trial Management Group.

Summary	Summary Details
----------------	------------------------

Information Type																												
Formulations	
 
Ad4-EnvCN54 at the dosage of <math>10^{10}</math> VP will be administered orally
 
MVA-CN54 at the dosage of <math>1.0 \times 10^8</math> TCID50 will be administered by IM needle injection
 
CN54gp140 at the dosage of 100<math>\mu</math>g will be administered with 5<math>\mu</math>g of MPLA in a liposomal formulation and administered by IM needle injection
 
Placebo 1: Capsule administered orally
 
Placebo 2: Buffered saline administered by I.M needle injection
 
																											
	
  
 Vaccine	Dosage Level(s)	Total Administered Volume (per site)	Route of Administration	
   
 Ad4-EnvCN54	<math>10^{10}</math>VP	Lyophilized powder in capsule	Oral	
 
 MVA-CN54	<math>1.0 \times 10^8</math> TCID50	0.5ml	I.M	
 
 CN54gp140 / MPLA + Liposome	100<math>\mu</math>g / 5<math>\mu</math>g	0.4 mL	I.M	
 
 Placebo	-	Powder in capsule	Oral	
 
 Placebo	-	0.5ml	I.M	
  
				Vaccine	Dosage Level(s)	Total Administered Volume (per site)	Route of Administration	Ad4-EnvCN54	$10^{10}$ VP	Lyophilized powder in capsule	Oral	MVA-CN54	$1.0 \times 10^8$ TCID 50	0.5ml	I.M	CN54gp140 / MPLA + Liposome	100 $\mu$ g / 5 $\mu$ g	0.4 mL	I.M	Placebo 	-	Powder in capsule	Oral	Placebo 	-	0.5ml	I.M
Vaccine	Dosage Level(s)	Total Administered Volume (per site)	Route of Administration																									
Ad4-EnvCN54	$10^{10}$ VP	Lyophilized powder in capsule	Oral																									
MVA-CN54	$1.0 \times 10^8$ TCID 50	0.5ml	I.M																									
CN54gp140 / MPLA + Liposome	100 $\mu$ g / 5 $\mu$ g	0.4 mL	I.M																									
Placebo 	-	Powder in capsule	Oral																									
Placebo 	-	0.5ml	I.M																									
Site:	
Clinical investigations will be carried out at the NIHR Imperial CRF, Hammersmith Hospital, Imperial College Healthcare NHS Trust.
 
Immunogenicity laboratory investigations will be performed in the Department of Infection and Immunity at Imperial College London, and safety laboratory investigations will be performed at Imperial College Healthcare NHS Trust.
																											
Aim:	
To explore the impact of different boosting options (MVA-C and protein) for oral Adenovirus serotype 4 vector prime expressing HIV-1 CN54 envelope (Ad4-EnvCN54) designed to optimize systemic and mucosal antibody response.
																											
Primary Objectives	
Part 1 & Part 2:
 
To evaluate the immunogenicity, safety and tolerability of oral Ad4 vector expressing HIV-1 CN54 envelope (Ad4-EnvCN54) when combined with different boosting options (MVA-CN54 and CN54gp140/MPLA) designed to optimise systemic and mucosal responses.
																											

Summary Information Type	Summary Details
Secondary Objectives	
Immunogenicity
 
Part 1 & Part 2:
 
To select conditions capable of promoting enhanced B cell responses based on

	
the following HIV-specific immune responses:
 
 
• Kinetics and magnitude of induced HIV-specific serum binding antibodies
 
• Kinetics and magnitude of induced HIV-specific mucosal binding antibodies (cervico-vaginal for women, semen for men and rectal and nasal for all)
 

Exploratory Objectives	
Immunogenicity
 
Part 1 & Part 2
 
To assess and characterize the following HIV-specific immune responses:
 
 
• HIV-specific neutralizing antibodies in the systemic compartment.
 
• Frequency and titer of serum binding antibodies to other HIV Env antigens (alternative clades) by ELISA or other assays.
 
• Characterisation of non-neutralising antibody function including Antibody Dependent Cellular Cytotoxicity (ADCC) and Antibody Dependent Cellular Viral Inhibition (ADCVI), Antibody dependent phagocytosis (ADCP), viral capture and aggregation assays.
 
• Anti-vector mediated immune responses i.e. anti-MVA-CN54 and anti_Ad4 antibody responses and functionality if present
 
• HIV-specific T-cell-mediated responses by ICS or Elispot analysis.
 
• Epitope mapping of B- and T-cell responses.
 
• Ex vivo analysis of colorectal biopsies (Part 2 participants only)
 
• PBMC ex-vivo HIV susceptibility assay
 

Summary Information Type	Summary Details
Primary Endpoints Measure(s)	
Part 1 & Part 2:
 
Immunogenicity
 
Antigen specific mucosal (cervico-vaginal for women, semen for men, and rectal

	
and nasal for all) antibody (µg/ml) responses two weeks after the final immunisation.
 
Safety and Tolerability:
 
 
• Proportion of participants with severe or greater (Grades 3-4) adverse reactions during the study
 
• Proportion of participants with vaccine-related serious adverse events (SAEs) throughout the study period
 

Secondary Endpoints Measure(s)	
Immunogenicity: Part 1 & Part 2
 
To assess the kinetics of immune responses elicited by each of the vaccine regimens:
 
 
• Frequency of serum and mucosal binding antibodies to HIV CN54gp140 antigen measured by binding ELISA.
 

Summary Information Type	Summary Details
Exploratory Endpoints Measure(s)	
Immunogenicity: Part 1 & Part 2
 
 
• Frequency and magnitude of HIV-gp140 specific B-cell-mediated responses in the systemic compartment measured by B-cell ELISPOT.
 
• Frequency, titer and avidity of serum binding antibodies to other HIV Env antigens (alternative clades) by ELISA or other assays.
 
• Frequency and titer of serum neutralising antibodies to homologous virus, and, if warranted a wider a panel of viruses representing different clades.
 

	
 
• Longevity of serum and mucosal responses at 12 months following final immunization
 
• Frequency and magnitude of HIV-specific T-cell mediated responses measured by T-cell and ICS (Intracellular Cytokine Staining).
 
• PBMC ex-vivo HIV susceptibility assay
 
• Measurement of CN54gp140 serum IgA responses over time
 
• Frequency and magnitude of T-cell chemokine and cytokine release following ex-vivo antigen stimulation quantified by Luminex.
 
• Epitope mapping of B- and T-cell responses
 
• Serum antibody responses to Ad4-EnvCN54 and MVA-CN54 as a marker of anti-vector immunity and vaccine “take”
 
• Ex vivo analysis of colorectal biopsies for activation markers by ICS (Part 2 only)
 
• Susceptibility of rectal biopsies to HIV-infection – infection assays
 
• Durability of responses will also be determined by measurement of response at weeks 26 (visit 9) and 48 (visit 11) of the trial schedule
 

Group selection	
Part 1:
 
Participants will be recruited and randomised into groups A-H with an oral and I.M placebo control (dependent on treatment allocation). This will be a participant blinded study where the participants are blinded to the group and dosing regime to which they are assigned. The laboratory undertaking immunological analysis will also be blinded to group and dosing regimen to prevent bias in analysis.
 
Part 2:
 
Participants will be randomised to the groups chosen for expansion. If only one group is expanded, there will be no randomisation. Participants will be blind to the vaccine regime group to which they have been assigned. The laboratory undertaking immunological analysis will also be blinded to group and dosing regimen to prevent bias in analysis.

Summary Information Type	Summary Details
Number of Participants to be Studied	
The study will enrol 48 participants to Part 1 and 12 participants for Part 2.
 
In Part 1, n=6 participants per group will be randomised to groups A-H.
 
In Part 2, n=6 participants will be vaccinated to the best responding regimes.
 
Recruitment will select potential participants who are willing to undergo serial

	blood draws. Additional participants may be enrolled to replace any early withdrawals.
Duration of Study Participation	Participants will be screened up to 90 days before the first vaccination and will be followed up for 24 weeks after the last vaccine administration. Excluding screening, participants will attend for 11 visits in 48 weeks.
Evaluation for Inter-Current HIV Infections	Participants will be tested for HIV according to the Trial Assessment Schedule (Table 2). Test results will be interpreted according to a pre-determined diagnostic algorithm. Should one or more serological HIV test(s) post-vaccination be positive, a nucleic-acid-based HIV test will be performed (if clinically indicated) to distinguish a true HIV infection acquired through exposure in the community from HIV seropositivity due to the vaccine-induced antibody response. HIV testing at additional time points may be performed upon request of the volunteer and Principal Investigator or designee as medical or social circumstances warrant.
Organisation	The Coordinating Center will be the Group of Mucosal Infection & Immunity at ICL. Drafting of the SAP will be lead by the Surrey Clinical Research Centre.
Safety Monitoring And Statistical Considerations	
Only a volunteer Trial ID, (and the Date of Birth) will identify collected CRF data. Safety will be continually monitored by the Investigators; pause criteria are pre-defined to facilitate consultation with the Trial Management Group prior to deciding on a permanent stop to protocol. Ad hoc safety review may be specifically requested by the Sponsor and the Principal Investigator, based on on-going review of the data.
 
At the end of the study, a Clinical Study Report (CSR) will be drafted. Safety and tolerability will be addressed by examining the overall rates of solicited and unsolicited adverse events and serious adverse events that might be associated with vaccination and the number of participants who experience these events. All clinical and routine laboratory data will be included in the safety analysis.

Summary Information Type	Summary Details
Sponsor	Imperial College London (ICL)
Sponsor Status	Non-Profit Organization
Funder	MRC UK
Chief/Principal Investigator	[name]
Chief Scientific	[name]

Investigator	
Clinical Trial Manager (Coordinating Center)	[name]
Clinical Trial Manager (ICRF – Clinical Site)	[name]
Lead Trial Nurse (ICRF – Clinical Site)	[name]

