## 7.6 CLINICAL STUDY DESIGN

To identify an effective Ad4 based oral vaccine that promotes systemic and mucosal responses to the HIV-1 envelope glycoprotein, our group will adopt a two part adaptive clinical trial. The study will assist in rapidly screening the impact of different routes, combination regimes and boosting options to Ad4-EnvCN54, MVA-CN54 and CN54gp140 / MPLA, to augment systemic and mucosal antibody responses following initial priming with Ad4.

The study will enrol 48 participants to Part 1 and 12 participants in Part 2. Recruitment will select potential participants who are willing to undergo serial blood draws. Additional participants may be enrolled to replace any early withdrawals.

**In Part 1**, n=6 participants per group will be randomised to groups A-H (Table 1). This design varies the number of Ad4 administrations, from 1 to 3, combined with either CN54gp140 protein boosts (A-D) or co-administration of gp140 with MVA (E-H). Groups A (gp140 alone) and E (MVA-CN54/CN54gp140 alone) will serve as control groups to assess the added benefit of the Ad4 vector. Each vaccine group (A-H) will be assessed for number of mucosal responders (mucosal antibody (rectal/genital/nasal) as measured by ELISA), and titre (mucosal and systemic) of antigen specific binding antibody. Based on data from the MUCOVAC2 study, in which participants received 3 intramuscular doses of CN54gp140 with GLA-AF adjuvant, we anticipate that there will be no mucosal responders in group A (although there will be detectable systemic responses). Enrolment through to completion of the primary immunological assessment for each group will be 7 months.

**In Part 2**, the best regimes from A-D (Ad4-EnvCN54/CN54gp140) and E-H (Ad4-EnvCN54/MVA-CN54/CN54gp140) will be expanded to n=12 (additional n=6) in Part 2. Immune responses at the Primary Immunogenicity Endpoint (Week 26) will be analysed. Selection will be based on total number of responders. In the event that more than one group has the same number of responders, mucosal antibody titre will be used to rank groups to determine which to take forward to Part 2. Should mucosal titers be indistinguishable between groups, then serum antibody levels will be taken into consideration in the selection of groups to progress to Part 2.

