#### **Intramuscular Placebo**

Intramuscular placebo for injection vials were developed by Polymun Scientific Ltd; Austria, to match the active MVA-C investigational product. The placebo comprises a liquid formulation containing 20 mM Tris / 0.15 M NaCl (pH 7.5). Tris is used as buffer substance, sodium chloride for appropriate osmolality and hydrochloric acid for buffer pH adjustment.

Investigational medicinal product vials and bottles will be labelled and packaged according to regulatory requirements. The PI will ensure that staff administering the vaccines have been appropriately trained in the written procedures for delivery of the vaccines.

Investigators and trained members of the clinical team will be encouraged to administer the vaccine as soon as possible and within 2 hours of being removed from cold storage. The date and time of administration will be recorded in the Case Report Form (CRF) and medical notes.

Participants will receive I.M injections, and Ad4 or placebo administered orally, as described in the schedule of doses (Table 1). In Part I, 36 participants will receive Ad4CN54-Env in combination with CN54gp140, or MVA-CN54 and CN54gp140, whilst 12 participants will receive an oral placebo in combination MVA-CN54 and/or CN54gp140. Dosing will be at weeks 0 (Month 0), 12 (Month 3) and 24 (Month 6). The two best vaccine regimes from B-D (Ad4/gp140) and F-H (Ad4/MVA-C/gp140), provided they meet the pass criterion, will be expanded and 12 participants will be screened and enrolled for Part 2 of the study.

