The study will enrol an additional 6 participants to two groups in Part 2 (Table 2). The best regimes from groups A-D (Ad4-EnvCN54 /CN54 rgp140) and/or E-H (Ad4-EnvCN54/MVA-CN54/CN54 rgp140) (if meeting the pass criteria) will be expanded to n=12.

The pass criteria for mucosal responders will be analysed in the first 32 participants (first four participants from each dosing group) at week 26 (the primary immunogenicity endpoint). The primary pass criteria will assess IgA responses in rectal mucosal samples, whereby a group will be considered to have met the pass criteria if there is a mucosal IgA titre greater than 100 ng/mL in the rectal secretions of ≥2 participants within a group at week 26.

However, if none of the groups meet this criterion, the selection will be expanded to include IgA responses from other mucosal secretions (nasal, cervico-vaginal (female participants) and semen (male participants)).

In the event that none/more than one of the groups meet this criterion, the selection will be based on week 26 median serum IgG titres. Statistical analysis comparing across groups A-D and E-H will be performed using the Kruskal-Wallis Test with Dunn's correction for multiple comparisons.

In the event that there is no statistical significance observed, the vaccination groups with the least and greatest exposure to the vaccine products (A and D) will be expanded into part 2 to allow for greater assessment of safety data.

4 Vaccination Schedule – Part 1 & Part 2

The doses, methods and schedule of immunisation are described below.

Table 1: Schedule of Doses and Method of Vaccinations

PART I							PART II	
	Group	N	Month 0	Month 3	Month 6		N	Vaccinations 1,2,&3
ARM 1	A	6	Oral placebo	CN54gp140 + Oral placebo +I.M placebo	CN54gp140 + Oral placebo +I.M placebo		12	Selected dosage from Part I
	B	6	Ad4-EnvCN54	CN54gp140 + Oral placebo +I.M placebo	CN54gp140 + Oral placebo +I.M placebo			
	C	6	Ad4-EnvCN54	CN54gp140 + Ad4-EnvCN54 +I.M placebo	CN54gp140 + Oral placebo +I.M placebo			
	D	6	Ad4-EnvCN54	CN54gp140 + Ad4-EnvCN54 +I.M placebo	CN54gp140 + Ad4-EnvCN54 +I.M placebo			
ARM 2	E	6	Oral placebo	CN54gp140 + MVA-CN54 + Oral placebo	CN54gp140 + MVA-CN54 + Oral placebo			
	F	6	Ad4-EnvCN54	CN54gp140 + MVA-CN54 + Oral placebo	CN54gp140 + MVA-CN54 + Oral placebo			
	G	6	Ad4-EnvCN54	CN54gp140 + MVA-CN54 + Ad4-EnvCN54	CN54gp140 + MVA-CN54 + Oral placebo			
	H	6	Ad4-EnvCN54	CN54gp140 + MVA-CN54 + Ad4-EnvCN54	CN54gp140 + MVA-CN54 + Ad4-EnvCN54			
		48					max 12	

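### The plan names three different candidate sets for Part 2, two of which leave a no-Ad4 control group eligible, and the SAP fallback expands control A by rule

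*Protocol*

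**What the plan says.** Seven statements in the current text define which groups compete for expansion, and they give three sets.

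- **B-D and F-H.** Protocol section 2, Study Design (Part 1 text): "one from B-D and one from F-H". Protocol 11.1, under Intramuscular Placebo, agrees: "The two best vaccine regimes from B-D (Ad4/gp140) and F-H (Ad4/MVA-C/gp140), provided they meet the pass criterion".
- **A-D and F-H.** Protocol section 2, Vaccine Schedule for Part 2: "The best regimes from A-D (Ad4-EnvCN54 / CN54gp140) and F-H".
- **A-D and E-H.** Protocol 7.6: "the best regimes from A-D (Ad4-EnvCN54/CN54gp140) and E-H". Protocol 10.1.2 and SAP 5.2 use the same ranges. SAP 3.2 has "The best regimes from groups A-D (Ad4-EnvCN54 /CN54 rgp140) and/or E-H", with an and/or that the other statements lack.

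Groups A and E receive oral placebo at every vaccination. Protocol sections 2 and 7.6 and SAP 3.1 name them as the controls against which the contribution of Ad4 is judged.

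The selection measure also matters. The protocol ranks on number of responders, then mucosal titre, then serum antibody. SAP 3.2 requires at least two participants in a group, among the first four per group, with rectal IgA above 100 ng/mL at week 26. It then turns to other mucosal sites. If none or more than one group qualifies, it compares median serum IgG. If no significance is found, groups A and D go forward to give more safety data.

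**The concern.** The choice decides which two regimens reach n=12. With three candidate sets in force, the same week 26 data could lead to different expansions, depending on which section is followed.

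What is lost depends on which control is chosen:

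- **A with one of F-H, or E with one of B-D.** The two expanded groups differ in both Ad4 and MVA. The Part 2 arm contrast in SAP 12.2.1.2 mixes the two effects, and the arm that contributed its control gains no further Ad4 data.
- **A with E.** Part 2 adds no Ad4 recipients, although the primary objective concerns Ad4.
- **A with D (the SAP fallback).** Both groups belong to Arm 1, so the planned Part 2 model, which has arm as its fixed effect, has no Arm 2 group.

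**Working it through.** **1. The plan's own figure.** Part 2 enrolment is 2 groups × 6 = 12, and the expanded groups total 2 × (6 + 6) = 24. Both match the protocol and SAP 12.2.1.2, and neither depends on the candidate set.

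**2. Possible pairs, one group per arm.**

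| Candidate set | Pairs | Pairs with a control | Share |
|---|---|---|---|
| B-D and F-H | 3 × 3 = 9 | 0 | 0% |
| A-D and F-H | 4 × 3 = 12 | A with F, G or H = 3 | 25% |
| A-D and E-H | 4 × 4 = 16 | 3 (A with F-H) + 3 (E with B-D) + 1 (A with E) = 7 | 43.75% |

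These shares are selection probabilities only for a ranking in which all four groups of an arm respond alike. A control is then first with probability 1/4 per arm, and 1 − (3/4)² = 0.4375 for at least one control when both are eligible.

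**3. Chance that a control ranks first in its arm on responder count.** The documents give no responder rates, so these are assumed. One control group and three Ad4 groups have independent binomial counts with n=6. The control wins if its count exceeds the largest Ad4 count. If it ties with k Ad4 groups at the top, it wins with probability 1/(1+k), that is, ties are split at random. Summing over all outcomes:

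| Control rate / Ad4 rate | Control first in its arm |
|---|---|
| 0% / 30% | 0.04% |
| 10% / 30% | 4.0% |
| 20% / 30% | 12.6% |
| 20% / 50% | 2.4% |
| 30% / 30% | 25% |

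The first row can be checked by hand. A control with no responders can only tie, when all three Ad4 groups also have none: (0.7⁶)³ × 1/4 = 0.1176³ × 1/4 ≈ 0.0004.

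**4. Chance that a control meets the SAP rectal IgA criterion.** For a response rate p, P(at least 2 of 4) = 1 − (1−p)⁴ − 4p(1−p)³. At p = 10% this is 1 − 0.6561 − 0.2916 = 5.2%. At 2%, 5%, 20% and 30% it is 0.2%, 1.4%, 18.1% and 34.8%.

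**5. The SAP fallback.** No probability is needed here: when no significance is found, A is expanded by rule and both expanded groups come from Arm 1.

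**The case against.** **The ranges may be loose arm names.** The brackets after A-D and E-H describe Ad4-containing regimens, which A and E are not, and the same ranges serve elsewhere as labels for the two arms. The authors may never have meant a control to compete. This is a fair reading of intent, but no sentence excludes A or E. The narrower range is written out in two places, and the mixed A-D/F-H statement fits neither reading. The SAP fallback sends A to Part 2 explicitly.

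**One body decides.** The Trial Management Group takes the decision, so different readers would not in practice act separately. It still needs to know which groups are eligible before it sees the data.

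**A control is unlikely to win.** The protocol expects no mucosal responders in group A. If that holds, A has almost no chance on responder count (0.04% in the first row of step 3). No such expectation is stated for E. The protocol does expect systemic responses in A, and serum antibody is the last tie-break in the protocol and a deciding step in SAP 3.2.

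**Two stronger readings are not supported.** A reader might infer that expanding a control would stop the Part 2 arm contrast from evaluating the Ad4 prime. That contrast does not isolate the prime under any set: under B-D/F-H both groups receive Ad4, and they differ in MVA and possibly in the number of Ad4 doses. The Ad4 effect rests on A against B-D and E against F-H. A reader might also take 25% and 44% as the chance that a control is expanded. The SAP rule is a threshold followed by tests and a fallback, not a best-of-four ranking. Suppose that Ad4 adds nothing, no group passes, and each arm has an independent 5% test (alpha for this step is not stated). Both tests are then non-significant with probability 0.95² ≈ 90%, and the fallback expands A but not E.

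Nor does including A and E in the Kruskal-Wallis comparison by itself make them eligible; they can be there as references.

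**Conclusion.** The inconsistency is real and can be confirmed by reading alone. Three candidate sets stand in current text, two of them literally admit a designated control, and the SAP fallback conflicts both with one group per arm and with the Part 2 arm model. How often a control would be expanded depends on unknown response rates: on responder count, from about 0.04% to 25% per arm over the rates tried, assuming independent groups, n=6 and random tie-breaking. The 25% and 44% figures are the equal-response case only. The point does not rest on these numbers, since a selection rule should give one answer from one dataset. For a Phase I selection design this should be corrected. It does not invalidate the Part 1 comparisons that address Ad4.

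**What to change.** State one candidate set, in identical words, in protocol section 2 (both statements), 7.6, 10.1.2 and 11.1 and in SAP 3.2 and 5.2. B-D and F-H already appears twice and is the set consistent with A and E being controls. Add a sentence saying that A and E stay in the comparisons as reference groups and are not candidates.

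In the same edit, reconcile the A-and-D fallback in SAP 3.2 with that set and with the Arm 1 versus Arm 2 analysis in SAP 12.2.1.2. Changing the letters alone would create a new contradiction inside SAP 3.2. One option is to label the fallback a safety-only exception and give it its own analysis.

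The cost is wording in both documents and one decision about the fallback. Part 2 enrolment stays at 12, and no further data are needed. If the selection has already been made, the SAP should record which set was applied.
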